Overall, the cediranib/olaparib combination demonstrated a significant clinical benefit over olaparib alone, as measured both by PFS and ORR. The increased clinical benefit of the cediranib/olaparib combination over olaparib monotherapy was greater in women with tumors that were not *gBRCAm* or who had a VUS status compared with women who harbored *gBRCA1/2* mutations. Toxicities were consistent with expected class-related toxicities of these drugs, with most common grade 3 or 4 toxicities attributed to each of the IPs including fatigue (27% cediranib/olaparib vs. 11% olaparib), diarrhea (23% vs. 0%), and hypertension (41% vs. 0%). There were 2 Common Terminology Criteria for Adverse Event (CTCAE) Grade 4 events, both in the cediranib/olaparib arm: 1 event of Grade 4 hypertension in a patient who was not fully compliant with blood pressure (BP) monitoring and 1 event of Grade 4 myelodysplastic syndrome (MDS).

Summaries of the clinical data in patients with recurrent ovarian cancer for cediranib/olaparib combination compared with single agent olaparib or cediranib are shown in [Table 3](#) and [Table 4](#), respectively.

Table 3 Comparison of cediranib/olaparib and single-agent olaparib in recurrent ovarian cancer trials

Patient characteristics	Treatment	Number of patients	PFS (months)	ORR (%) by RECIST	Reference
gBRCAm (N=47);	Olaparib single agent 400 mg bd	46	9.0	56.1	Liu et al 2014
gBRCAwt (N=43) all platinum-sensitive	Cediranib 30 mg od plus olaparib 200 mg bd	44	17.7	83.7	
all gBRCAm ; all partially platinum sensitive	Olaparib 200 mg bd	32	6.5	25	Kaye et al 2012
	Olaparib 400 mg bd	32	8.8	31	
	PLD 50 mg/m ²	33	7.1	18	
gBRCAm (N=17); non- gBRCAm (N=46)	Olaparib 400 mg bd; platinum-sensitive patients	25	N/A	52	Gelmon et al 2011
	Olaparib 400 mg bd; platinum-resistant patients	38	N/A	13	
	Olaparib 400 mg bd; platinum resistant (non- gBRCAm only)	26	N/A	4	

Abbreviations: bd twice daily; *gBRCAm* germline *BRCA* mutant; *gBRCAwt* germline *BRCA* wild type; N/A not available; N number of subjects; od once daily; ORR objective response rate; PFS progression free survival; PLD Pegylated liposomal doxorubicin; RECIST Response Evaluation Criteria in Solid Tumors; VUS variant of unknown significance.

Note: these studies used the capsule formulation of olaparib.

Table 4 Comparison of cediranib/olaparib and single-agent cediranib in recurrent ovarian cancer trials

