6.8.3 Management of cediranib-related toxicity

6.8.3.1 Hypertension

Only doses of cediranib will be modified for hypertension; olaparib doses will not be reduced unless other toxicities are experienced.

In clinical trials, increases in BP have been reported within a few hours of starting cediranib. Since rapid changes in blood pressure can occur with cediranib treatment, with the potential for life-threatening complications if hypertension is not appropriately managed, all patients should check their BP twice daily for at least the first 8 weeks after starting cediranib, or, if antihypertensive management is required, until a stable anti-hypertensive regimen has been established, even if this requires more than 8 weeks. After 8 weeks or once a stable regimen has been achieved, BP monitoring may be reduced to once daily. Twice daily monitoring should be re-implemented after any cediranib dose interruption for 2 weeks or until the patient is re-established on a stable antihypertensive regimen, whichever takes longer.

Patient BP will also be measured during routine study visits: weekly during the first 4 weeks, every 2 weeks during the next 4 weeks and every 4 weeks thereafter, to ensure that BP guidelines are being correctly followed. Increase in BP should be treated promptly with standard antihypertensive therapy, ensuring that the maximum recommended dose and number of antihypertensive medicinal products is reached before considering cediranib dose adjustment. See Appendix G for suggested antihypertensive medications by class. Patients may have up to 4 drugs for management of hypertension prior to any dose reduction in cediranib.

If patients require a delay of > 3 weeks for management of hypertension, discontinuation of cediranib or protocol therapy may be considered after discussion with the PI and the AstraZeneca study physician. In case of persistent or severe hypertension, despite the optimal use of antihypertensive medicinal products and cediranib dose reduction, cediranib should be permanently discontinued.

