
Recurrent or persistent (>24 hours) or symptomatic increase by >20 mmHg (diastolic) or to > 140/90 mmHg if previously within normal limits.
 
Monotherapy may be indicated
	
Initiate BP medication for first line treatment. Suggestions: ACE inhibitor or Calcium Channel Blocker
 
Escalate dose of medication in step wise fashion until BP is controlled or at a maximum dose
 
If BP is not controlled to <140/90 mmHg with one “maximized” drug regimen, then add a second agent.
 
Study drug does not need to be held unless otherwise clinically necessary
 
Consider renal consult
	
Increase frequency of monitoring until stabilized to BP <140/90 mmHg
	
Do not withhold cediranib unless otherwise clinically necessary

Table 12 Hypertension Monitoring and Management

Event	Antihypertensive Therapy	Blood Pressure Monitoring	Cediranib Dose Modification
Requiring more than one drug or more intensive therapy than previously.	
Maximize 2 drug regimen
 
Suggestions: ACE-inhibitor + Calcium Channel Blocker
 
Escalate doses of existing medication until BP is controlled or at a maximum dose.
 
If BP is not controlled to <140/90 mmHg with two drug regimen, then add a third agent.
 
Study Drug will not be held during trial of two drug combinations. Additional antihypertensive drugs, up to a total of 4, may be maximized for BP control.
 
Consider consult with a BP management specialist if greater than 3 drugs are required for BP control.
	Increase frequency of monitoring until stabilized to BP <140/90 mmHg	
Do not withhold cediranib unless BP is not decreased to less than 150/100 mmHg 48 hours after multi-drug therapy is instituted or if clinical symptoms worsen (eg, headache).
 
If BP is not controlled to less than 150/100 mmHg with maximal therapy or if clinical symptoms worsen, then withhold cediranib (up to 3 weeks) until maximum effect of the antihypertensive agents is achieved.
 
If BP is reduced to Grade 1 within 3 weeks, cediranib may be resumed at prior dose.

Table 12 Hypertension Monitoring and Management

Event	Antihypertensive Therapy	Blood Pressure Monitoring	Cediranib Dose Modification

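### One row of protocol Table 12 says both to withhold cediranib and not to withhold it when symptoms worsen during a two-drug antihypertensive trial

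*Protocol*

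**What the plan says.** The row at issue is the third event row of Table 12 in protocol Section 6.8.3.1. It bears on withholding cediranib in two columns.

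- **Antihypertensive Therapy column.** The site maximises a two-drug regimen, then: "If BP is not controlled to <140/90 mmHg with two drug regimen, then add a third agent". On study treatment: "Study Drug will not be held during trial of two drug combinations". On further agents: "Additional antihypertensive drugs, up to a total of 4, may be maximized for BP control".
- **Cediranib Dose Modification column, first sentence.** "Do not withhold cediranib unless BP is not decreased to less than 150/100 mmHg 48 hours after multi-drug therapy is instituted". The sentence adds worsening clinical symptoms, with headache as the example, as a second exception.
- **Cediranib Dose Modification column, second sentence.** "If BP is not controlled to less than 150/100 mmHg with maximal therapy or if clinical symptoms worsen, then withhold cediranib". The hold may last up to 3 weeks, and cediranib may be resumed at its previous dose if blood pressure falls to Grade 1 in that time.

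The text of Section 6.8.3.1 above the table asks for prompt treatment of raised blood pressure, "ensuring that the maximum recommended dose and number of antihypertensive medicinal products is reached before considering cediranib dose adjustment".

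**The concern.** The two cells are meant to be read together for one patient at one visit. One forbids a hold throughout a two-drug trial. The other makes worsening symptoms a reason to hold, whatever the number of agents. A site that follows either cell departs from the other.

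The stakes are mainly clinical. Section 6.8.3.1 itself warns that pressure can rise quickly on cediranib and that poor management can endanger life. Among the grade 3 or 4 toxicities that Section 1.1.4.3 lists for the combination in the earlier randomised phase II study, hypertension has the highest rate, at 41%. The synopsis plans about 60 patients at about 40 sites, which is 60 / 40 = 1.5 patients per site on average. Most sites would meet this situation rarely, if at all, and would have to interpret the row alone.

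There is also a reporting consequence. The SAP summarises dose interruptions and actual exposure (3.3.1, 4.2.6), relative dose intensity (3.3.2) and adverse events leading to interruption (4.2.9). If sites read the row differently, those summaries partly describe the reading and not the drug.

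**Working it through.** No sample size, power or event count is involved, so the check applies each statement to the same patient state.

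**Does the therapy-column sentence cover cediranib?** Yes. In the row above, the therapy column says study drug need not be held unless clinically necessary, and the dose column says the same of cediranib by name. Section 6.8.3.1 also opens by saying that hypertension leads to changes in cediranib doses only. Study drug in this table therefore includes cediranib.

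**Statements.**
- A: therapy column, no hold during a two-drug trial.
- B: dose column, first sentence, no hold unless pressure is not below 150/100 mmHg at 48 hours of multi-drug therapy, or symptoms worsen.
- C: dose column, second sentence, hold if pressure is not below 150/100 mmHg on maximal therapy, or symptoms worsen.

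| State | A | B | C | Result |
|---|---|---|---|---|
| 1. Two-drug trial, symptoms worsening | No hold | Bar lifted | Hold | A and C cannot both be followed |
| 2. Two-drug trial, 48 hours, 165/105 mmHg, symptoms not worsening, regimen not maximal | No hold | Bar lifted | Not triggered | Continuing and escalating breaches nothing; unclear whether a hold is permitted |
| 3. Three agents, 48 hours, not below 150/100 mmHg, symptoms not worsening, regimen not maximal | Silent | Bar lifted | Not triggered | A hold is not barred but not ordered; no guidance between the two |

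**State 1** is a contradiction. It does not turn on what multi-drug or maximal means, because worsening symptoms are a separate trigger in both B and C.

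**States 2 and 3** are ambiguities. The pressure in state 2 is below the limits of the next row (systolic 180 or diastolic 110 mmHg), so that row's plain instruction to withhold does not apply. B is a conditional prohibition: meeting its condition removes a bar and orders nothing. On blood-pressure grounds, the order to hold in this row comes only from C.

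**Why the undefined terms matter.** Multi-drug therapy naturally includes two drugs, which would let B operate while A still forbids a hold. Maximal therapy could mean the maximised two-drug regimen that this row calls for, or the full set of up to four agents that it allows. C is reached at different points under the two readings.

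**The case against.** **Other text may settle it.** Section 6.8 gives investigators discretion to hold one drug when a toxicity is attributed to that drug alone. Table 12 is introduced as guidance, and a site looking for a hold rule would naturally turn to the dose column first. A reader could also treat the symptom trigger as a specific exception to a general rule. These points lower the practical risk, but none ranks the cells. Discretion would let one site hold and another not. The row above writes its exception into both columns, so the lack of one in the two-drug sentence is conspicuous.

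**Three competing triggers.** A reader might infer that the plan sets three incompatible hold rules: never on two drugs, at 48 hours, and only after maximal therapy. The documents do not support that. The 48-hour sentence permits and the maximal-therapy sentence requires, so they can be read as stages, though the row does not say so. The maximal-therapy sentence does not say that holds are confined to that point, and symptoms are a separate trigger. The patient at 165/105 mmHg without worsening symptoms can be managed without breaching any sentence.

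**The body text as a further conflict.** The Section 6.8.3.1 instruction to exhaust antihypertensives before adjusting cediranib most naturally concerns dose reduction. Its paragraph ends by allowing up to four drugs ahead of any reduction, Section 6.8 separates holding from dose modification, and this row lets a withheld drug resume at its previous dose. It should not be counted as a rival rule on withholding.

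**Conclusion.** The row is wrong as written in one respect: opposite instructions on withholding cediranib for a patient on a two-drug trial with worsening symptoms. This rests only on study drug including cediranib, which the table and section text support. The undefined terms and the unstated relation between the 48-hour and maximal-therapy sentences are a secondary defect of clarity.

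The number of patients affected cannot be derived. A reader might apply the 41% to the planned sample, 0.41 x 60 = 24.6, and infer that about 25 patients are exposed. That figure would count all grade 3 or 4 hypertension, including patients under the next row, where the instruction is plain. It also comes from a platinum-sensitive population given olaparib capsules. It does not estimate how many patients worsen symptomatically during a two-drug trial.

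The consequence is for patient safety and for consistency across sites. In the analysis it reaches the interruption, exposure, dose-intensity and adverse-event summaries, which are descriptive and, in a single-arm study, involve no comparison between arms. Nothing in the documents shows an effect on the objective response rate by central review.

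**What to change.** The sponsor's clinical team should:

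1. Reconcile the therapy and dose cells of this row so that they give one instruction for a patient on a two-drug trial whose symptoms worsen.
2. State whether the symptom condition and the 48-hour condition apply during a two-drug trial.
3. Define multi-drug therapy and maximal therapy, and say whether the 48-hour and maximal-therapy sentences are successive stages.
4. Send sites a clarification.

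Which rule stands is for that team; none is proposed here. The cost is wording in one table row and a site communication. No assessment, sample-size figure or analysis changes.

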6.8.3.2 Diarrhea

Diarrhea is often observed with cediranib. Diarrhea usually starts early (within the first 4 weeks of treatment), however, it can occur at any time during treatment. Management of diarrhea should start at the first sign of diarrhea. Loperamide and advice on how to manage diarrhea should be readily available to patients from the start of cediranib treatment so that they can be applied at first episode of diarrhea. Active and early management of diarrhea is recommended even with Grade 1 diarrhea. Management is as shown in Table 13:

Table 13 Management of Diarrhea

Toxicity	Management/Modifications
Initial grade 1 or 2 diarrhea	
Patients should start loperamide (per standard practice) and continue to take loperamide until patients are free from diarrhea for at least 12 hours. The dose of loperamide should not exceed 16 mg in a 24-hour period. Patients should also be counselled to start a BRAT diet.
 
If diarrhea persists despite 24 hours of loperamide treatment, withhold cediranib for a maximum of 7 days, continue loperamide, and maintain hydration. Cediranib may be restarted at the same dose once patients have been free from diarrhea for 12 hours.
 
Patients should be instructed to contact their study physician if mild or moderate (NCI CTCAE Grade 1 or 2) diarrhea persists for over 48 hours despite treatment with loperamide and cediranib dose interruption.

Table 13 Management of Diarrhea

Toxicity	Management/Modifications
For either persistent grade 2 diarrhea or grade 3 or 4 diarrhea	Patients with persistent or severe diarrhea (NCI CTCAE Grade 3 or higher) may also require dose reduction or discontinuation of therapy with cediranib, follow guidance in Table 7

Abbreviations: BRAT bananas, rice, applesauce, toast; CTCAE Common Terminology Criteria for Adverse Event; NCI National Cancer Institute.

6.8.3.3 Fatigue

Fatigue is a common adverse drug reaction reported for both cediranib and olaparib. Fatigue experienced by patients taking cediranib may be rapid in onset. During clinic visits, patients fatigue levels should be discussed. Patients should seek medical advice early if Grade 2 fatigue develops (moderate fatigue causing difficulty performing some activities of daily living).

Care should be taken to ensure that the nutritional status of the patients is optimized and patients should be encouraged to drink plenty of fluids. Patients should be encouraged to manage fatigue by alternating periods of rest with light aerobic exercise, which may improve the symptoms in some cases.

Consideration should be given to other possible causes of fatigue (eg, thyroid function, depression/insomnia and other concomitant medicinal products). Additionally, short interruption of cediranib dosing (initially 2-3 days-or longer-up to a maximum of 21 days) may help relieve fatigue. When symptoms improve cediranib should be restarted with the same dose or, if necessary, a dose reduction can be considered.

6.8.3.4 Proteinuria

Proteinuria is a common adverse reaction reported for cediranib and if this occurs during treatment, it should be managed according to [Table 14](#). For management of suspected cases of nephrotic syndrome, refer Section [5.2.1.4](#).

Table 14 Management of Proteinuria

Proteinuria Value if following by urinalysis	Monitoring	Dose modification
Greater than 2+ AND Creatinine $\leq 1.5x$ ULN	Perform UPC	Continue study drugs at planned dose
Greater than 2+ AND Creatinine $> 1.5x$ ULN	Perform UPC	Interrupt cediranib until results of UPC are known (see below)
Based on results of the UPC^a		
UPC ≤ 1.0	Continue monitoring according to Schedule of Assessments (Table 5)	Continue study drugs at planned dose
UPC > 1.0 and ≤ 3.5 AND Creatinine $\leq 1.5x$ ULN	Perform UPC at each routine visit	Continue study drugs at planned dose
UPC > 3.5 OR Creatinine $> 1.5x$ ULN	Perform UPC at each routine visit	Interrupt cediranib for up to 21 days and repeat UPC and creatinine assessment. If UPC resolves to < 3.5 and creatinine to $\leq 1.5x$ ULN, resume cediranib with reduction in cediranib by one dose level. Consider consultation with nephrologist

^a If UPC is < 1.0 and creatinine $> 1.5x$ ULN, AE management should be followed as described above
Abbreviations: ULN upper limit of normal; UPC urine protein:creatinine ratio

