6.8 Management of IP related toxicities

The dose levels and the general approach to dose modification of the cediranib and olaparib component of the combination therapy are shown in Table 7 and Table 8, respectively. Specific dose modification information for some AEs are provided in Section 6.8.3 and Section 6.8.4. Please refer to the current IBs for emerging safety data for cediranib and olaparib: CCI

AEs should be treated with the appropriate maximum supportive care, and dose reductions should be clearly documented in the eCRF.

Table 7 Dose modification cediranib

Dose Level	Cediranib tablets
Initial dose	30 mg daily
Dose reduction 1	20 mg daily
Dose reduction 2	15 mg daily

Table 8 Dose modification of olaparib

Dose Level	Olaparib tablets
Initial dose	200 mg twice daily
Dose reduction 1	150 mg twice daily
Dose reduction 2	100 mg twice daily

At the discretion of the investigator, the study drugs may be held or dose modified independently if the observed toxicity is attributed to only one of the drugs, while the patient continues to receive the drug not associated with the observed toxicity. The time a given drug is held should not exceed 3 weeks. Once dose of study drug(s) have been reduced, no dose re-escalation is permitted.

If treatment has to discontinue due to toxicity, both IPs (cediranib and olaparib) should be discontinued at the same time; patients are not allowed to remain in the study if they are taking either cediranib or olaparib as monotherapy. However, in rare circumstances, patients experiencing ongoing clinical benefit but who develop one of the toxicities listed below related to one of the IPs that prevents them to continue to take this IP, may be allowed to continue on the unrelated drug if in the opinion of the treating investigator the risk benefit remains favorable and only after discussion with the AstraZeneca Study Physician and the Principal Investigator.

AEs requiring cediranib to be discontinued:

- GI perforation
- Arterial Thromboembolic Event
- PRES
- Severe hemorrhage
- Severe persistent hypertension despite maximal anti-hypertensive treatment

AEs requiring olaparib to be discontinued:

- Bone marrow findings consistent with MDS/ AML
- Severe persistent anemia
- Pneumonitis

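### Protocol Table 14 gives two opposite cediranib instructions when UPC is at or below 1.0 and creatinine is above 1.5x ULN, and footnote a does not say which applies

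*Protocol*

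**What the plan says.** Table 14 in Protocol Section 6.8.3.4 works in two stages.

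The upper stage starts from a dipstick result greater than 2+ and calls for a UPC. If creatinine is at or below 1.5x ULN, dosing continues. If creatinine is above 1.5x ULN, the instruction is "Interrupt cediranib until results of UPC are known (see below"), which passes the decision to the lower stage.

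The lower stage has three rows:

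- UPC at or below 1.0, with no mention of creatinine: "Continue monitoring according to Schedule of Assessments" and "Continue study drugs at planned dose".
- UPC above 1.0 and up to 3.5, with creatinine at or below 1.5x ULN: continue at the planned dose, with UPC at each routine visit.
- A row that opens "UPC > 3.5 OR Creatinine" and sets the creatinine limit at more than 1.5x ULN: "Interrupt cediranib for up to 21 days and repeat UPC and creatinine assessment". If UPC falls below 3.5 and creatinine to 1.5x ULN or less, cediranib resumes one dose level lower.

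Footnote a is attached to the heading of the lower stage, not to a row. Its condition begins "If UPC is < 1.0 and creatinine" and is completed by creatinine above 1.5x ULN. Its instruction is "AE management should be followed as described above".

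Section 6.8 adds: "Once dose of study drug(s) have been reduced, no dose re-escalation is permitted".

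**The concern.** The first and third UPC rows are not mutually exclusive. The second row has an explicit creatinine limit and the first has none, so nothing in the table confines the first row to patients with acceptable creatinine. The third row is joined by OR, so creatinine alone is enough to trigger it at any UPC.

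The footnote shows that the authors had this combination in mind, but it sends the reader to text above it, and several instructions stand there. Two sites with the same laboratory results could act in opposite ways, each with a row of the protocol to support it. One continues cediranib unchanged. The other holds it for up to 21 days and, on recovery, restarts one level lower with no way back up.

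That is first a matter of consistent patient management. It also feeds the SAP summaries of interruptions, reductions and relative dose intensity (SAP Sections 3.3.2 and 4.2.6). Protocol Section 4.5 keeps the dose-modification rules in force for patients treated beyond the final protocol visit.

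**Working it through.** There is no planned figure to reproduce here. The check is whether the three UPC rows divide all patients cleanly.

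**Inputs (Protocol Table 14).** Let u be UPC and c be creatinine as a multiple of ULN.

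| Row | Condition | Cediranib |
|---|---|---|
| R1 | u ≤ 1.0 | continue |
| R2 | 1.0 < u ≤ 3.5 and c ≤ 1.5 | continue |
| R3 | u > 3.5 or c > 1.5 | interrupt |

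**Overlaps.**

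- R1 and R2: none, because the UPC ranges do not meet.
- R2 and R3: none, because R2 excludes both triggers of R3.
- R1 and R3: u ≤ 1.0 and (u > 3.5 or c > 1.5). The first alternative is impossible, which leaves u ≤ 1.0 and c > 1.5.

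**Gaps.** None. u ≤ 1.0 is in R1. For 1.0 < u ≤ 3.5, R2 covers c ≤ 1.5 and R3 covers c > 1.5. u > 3.5 is in R3.

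**Grid check.** With UPC at 0.5, 1.0, 1.1, 2, 3.5 and 4 and creatinine at 1.0, 1.5, 1.6 and 2.5x ULN there are 6 × 4 = 24 cells. Twenty match exactly one row. Four match two rows with opposite instructions:

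| UPC | Creatinine (x ULN) | Rows met | Footnote a condition met? |
|---|---|---|---|
| 0.5 | 1.6 | R1 continue, R3 interrupt | yes |
| 0.5 | 2.5 | R1 continue, R3 interrupt | yes |
| 1.0 | 1.6 | R1 continue, R3 interrupt | no |
| 1.0 | 2.5 | R1 continue, R3 interrupt | no |

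**Does anything else in the Protocol settle it?**

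- Footnote a: the text above it includes the urinalysis rows, R1, R3 and, further back, the general non-hematologic rules in Table 11 (Section 6.8.2). It names none of them.
- Table 11 is based on toxicity grade and mentions neither UPC nor creatinine.
- Section 6.8.3.14 asks for caution in mild or moderate renal impairment and for a cediranib adjustment to be considered if there are signs of toxicity. It does not choose between the rows.
- Section 6.8.4.4 concerns olaparib and creatinine clearance.

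**Size of the dosing difference (Table 7).** From the starting dose, one level down is 30 to 20 mg daily, (30 − 20)/30 = 33% lower. From the first reduced level it is 20 to 15 mg, (20 − 15)/20 = 25% lower. Either applies only if the resumption criteria are met.

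**The case against.** The strongest reply is that very few patients can reach the conflict. By the table's own route a patient needs a dipstick above 2+, then a UPC at or below 1.0 despite it, and creatinine above 1.5x ULN as well. Section 5.2.1.4 allows a UPC where appropriate, so other routes exist, but the group could be empty among about 60 patients. That stands.

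A reader might infer from Section 7.7 that creatinine rises with little proteinuria are to be expected, because both drugs can affect creatinine handling, and might put the number at about 3 patients (0.044 × 60 = 2.6). The documents do not support that. The 4.4% counts any creatinine increase at cediranib 20 mg daily. The same passage calls those increases mild and the clinical impact small. No rate is given for 30 mg with olaparib, or for creatinine above 1.5x ULN with a dipstick above 2+ and a low UPC. Many patients with a creatinine rise alone would not meet the dipstick condition.

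The footnote also does some work. It would have no purpose if the low-UPC row applied unchanged, so it warns a careful site not to act on that row alone. It does not say what to do instead, so the ambiguity remains.

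Finally, sites have other safeguards: prompt retesting when creatinine clearance falls below 50 mL/min (Section 6.8.4.4) and access to sponsor medical staff (Sections 6.4 and 9.2). These lessen the risk but do not resolve the two rows.

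**Conclusion.** The contradiction is real. It is the only overlap among the UPC rows and is confined to UPC at or below 1.0 with creatinine above 1.5x ULN. Footnote a names the combination without resolving it and misses UPC exactly 1.0.

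The likely reach is small, and the documents give no basis for a count. No sample size, power or primary-analysis figure depends on it. It is worth correcting because a stated dosing rule contradicts itself, the two actions are opposite, and one of them can lead to a reduction that Section 6.8 does not allow to be reversed.

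A reader might take the consequence to be 30 mg uninterrupted against a permanent 20 mg. That holds only for a patient still at the starting dose whose UPC and creatinine then meet the resumption criteria.

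The conclusion rests on reading the table conditions literally. It takes no view on which instruction is right.

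**What to change.** The sponsor should reconcile the two rows and footnote a so that:

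- every combination of UPC and creatinine falls in exactly one row, with none left uncovered;
- footnote a names the row or table that applies;
- footnote a uses the same UPC cut-off as the row.

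Which action applies is the sponsor's clinical decision.

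The revised rows should be checked for gaps as well as overlaps. For example, replacing OR by AND in the last row removes the overlap but leaves UPC 2 with creatinine 1.8x ULN, and UPC 4 with creatinine 1.2x ULN, in no row.

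The cost is a small edit to one table and its footnote, made by protocol amendment or a letter to sites. No analysis changes.
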